### **11.2 Schedule of Examinations**

#### **11.2.1 Study Visits and Phone Follow-up**

Table 1 displays the required schedule for subject treatments and evaluations for Test and Control Groups. Sites participating in this study have been selected upon their capabilities to successfully carry out those assessments. Subjects will need to return to the hospital for a follow-up clinical visit at 3 months, 6 months, 1 year, 2 years and 3 years. Follow-up by phone will be conducted for all subjects at 9 months, 18 months and 30 months. Arrhythmia monitoring assessments, as described in Table 1, will be discontinued once subjects have progressed to persistent AF/AT.

All subjects will be followed through 3-years. Subjects who reach the primary endpoint (progress to persistent AF/AT) will only have to return for the final visit at 3 years; however, they will be followed for safety through the 3-years study period by their hospital and all adverse events are to be reported by the investigator as per protocol requirements. Subjects in the Test Group who undergo a repeat ablation procedure will continue follow-up according to the schedule of their index (first) ablation procedure. Thus, subject visits will be counted from the time of the index ablation procedure and not from the date of the repeat ablation procedure. Subjects in the Control Group who undergo an ablation procedure (cross-over), will continue follow-up according to their initial schedule.

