### **11.4 Management of Arrhythmia Recurrence During Follow-up**

#### **11.4.1 Arrhythmia Recurrence: Test Group**

Each investigator's routine clinical practice is to be followed as closely as possible regarding management of arrhythmia recurrence. If a subject undergoes re-ablation(s) for arrhythmia recurrence, the decision should be made in accordance with current AF management guidelines. All re-ablation procedure(s) must be fully documented. If a determination is made that progression to persistent AF/AT has occurred, no further arrhythmia monitoring (TTM, ECG, etc) will be required. After reaching the study endpoint, test subjects do not need to return for interim follow-up visits. These subjects will only have to return for the final visit at 3 year. However, they will be followed through the 3 years for safety by their hospital and all adverse events are to be reported by the investigator as per protocol requirements.

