#### **11.4.2 Arrhythmia Recurrence: Control Group**

The investigator's routine clinical practice is to be followed as closely as possible regarding management of arrhythmia recurrence. Changes in AAD treatment are allowed if needed; however, changes should be made in accordance with current AF management guidelines. If an investigator determines that progression to persistent AF/AT has taken place regardless of AAD regimen no further arrhythmia monitoring (TTM, ECG, etc) will be required. After

---

e Medication management includes reviewing all medications taken and an attempt to identify drugs with possible incompatibility with AAD medication(s); review and manage drug taking routine: timing - warning about taking drugs too close together or too far apart; warning about drug holidays and dangers; discuss taking with or without food, as prescribed; coach to use robust routines (taking pills same time each day); pill organizers; and/or recruitment of family to assist subject.

reaching the study endpoint, control subjects do not need to return for interim follow-up visits. These subjects will still be followed for safety until the 3-year follow-up visit has taken place.

If Control Group subjects are to undergo RF ablation (crossover) while not having reached the primary endpoint, they will continue follow-up through 3 years (refer to Appendix B for details regarding crossover management). If crossover subjects experience AF recurrence, the investigator will assess whether a change in AAD(s) treatment is required, if repeat ablation is appropriate, or if progression to persistent AF/AT has occurred. If a determination is made that progression to persistent AF/AT has occurred, no further arrhythmia monitoring (TTM, ECG, etc) will be required. After reaching the study endpoint, crossover subjects do not need to return for interim follow-up visits. These subjects will still be followed for safety until the 3-year follow-up visit has taken place.

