8.3 Derived Variables

Duration of AF [months]

Time between the recorded date of first AF and the date of randomization.

Time to persistent AF/AT

According to protocol, persistent AF/AT is defined as AF/AT lasting longer than 7 consecutive days or requiring termination by cardioversion after 48 hours. The primary endpoint is reached at the date of the first cardioversion after randomization (except cardioversion solely as part of a (re-)ablation procedure) or detection of persistent AF/AT by transtelephonic monitoring (TTM, performed between month 3 and month 36). The sponsor will review and adjudicate all events (progressions to persistent AF/AT), which were reported by the Investigator. Adjudication will already be performed for the interim analyses. All events where the sponsor confirmed in their final assessment that the primary endpoint was reached will be taken into account for analysis. The date at which the primary endpoint was reached will be taken as adjudicated by the sponsor or as reported by the Investigator (if no sponsor adjudicated date is available).

The protocol is not specific about the start date for time to event calculation. Originally according to SAP version 1.0 (which was applied for the interim analyses) time to event had been defined as the difference between randomization date and the date at which the endpoint was reached. However, after further discussion, it was decided to update the start date for time to event calculation for final analysis and to use date of procedure as start date for the test group, and date of randomization as start date for the control group.

This approach seems to be more appropriate and more conservative, as visit windows are calculated from date of procedure for test group. Otherwise, if time to event was calculated from date of randomization, test group would have longer follow-up period and longer time to each follow-up visit as control group.

If the primary endpoint is not observed during follow-up time, subjects will be regarded as censored at the completion visit/ last visit or at the last time TTM was recorded, whichever is later.

Time to persistent AF (HRS 2017)

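### Required rhythm monitoring ends when the site determines progression, but only sponsor-confirmed events count, so a subject whose event is not confirmed stays in the primary analysis as event-free without scheduled rhythm monitoring

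*SAP*

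**What the plan says.** **When monitoring stops.** Protocol 11.2.1 states the general rule: arrhythmia monitoring assessments "will be discontinued once subjects have progressed to persistent AF/AT". For the Control Group, 11.4.2 names the person who decides: "If an investigator determines that progression to persistent AF/AT has taken place regardless of AAD regimen no further arrhythmia monitoring" is required. For the Test Group, 11.4.1 leaves that person unnamed: "If a determination is made that progression to persistent AF/AT has occurred, no further arrhythmia monitoring (TTM, ECG, etc) will be required". For crossovers, 11.4.2 has the investigator assess whether progression has occurred.

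**What remains afterwards.** Protocol 11.2.1: "Subjects who reach the primary endpoint (progress to persistent AF/AT) will only have to return for the final visit at 3 years". Section 11.4.1 repeats this for the Test Group: "After reaching the study endpoint, test subjects do not need to return for interim follow-up visits". Safety follow-up and adverse event reporting continue.

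**What counts as an event.** SAP 8.3 has the sponsor adjudicate the progressions that investigators report: "All events where the sponsor confirmed in their final assessment that the primary endpoint was reached will be taken into account for analysis".

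**When other subjects are censored.** SAP 8.3: if no endpoint is observed, "subjects will be regarded as censored at the completion visit/ last visit or at the last time TTM was recorded, whichever is later".

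**The concern.** The person who stops monitoring and the person who decides whether an event counts are different, and neither document says what happens when they disagree. If the sponsor does not confirm a reported progression, the subject has no event. The only censoring rule then carries that subject forward to the last visit or last TTM, whichever is later. The time between the site's call and that visit enters the log-rank risk set as observed event-free time, although the monitoring meant to detect the endpoint was no longer required.

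Two things are at stake. True later events may be missed, which costs power. And if site calls or overrulings are distributed differently between arms, the treatment comparison is biased. The trial is open label, the sponsor adjudicates, and Protocol 15.5 makes a Clinical Endpoint Committee optional. As SAP 8.3 is written, adjudication covers investigator-reported events only, so it can remove reported events but has no stated route to add unreported ones.

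**Working it through.** **1. Following one subject through the rules.**
- The site determines progression: required TTM, ECG and interim visits end (Protocol 11.2.1, 11.4.1, 11.4.2).
- The sponsor does not confirm: no event is counted (SAP 8.3).
- The subject attends a later visit: censored event-free at that visit (SAP 8.3).

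No section delays the stop until adjudication, restarts monitoring after an unconfirmed call, or censors at the last rhythm recording. SAP 8.3 has a fallback for a missing adjudicated date but none for an unconfirmed event. SAP 8.2 relies on the log-rank test to handle censoring, which does not help when the censoring date lies later than the rhythm observation.

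**2. Disagreement is foreseeable from the text.** The TTM instructions under Protocol 11.2.1 stop TTM once AF has been present for 7 consecutive days, whereas the endpoint in 10.1 requires more than 7. A site can follow the stop rule before the endpoint definition is met. SAP 8.3 also dates the endpoint at the first cardioversion after randomization without repeating the 48-hour condition in that sentence, although Protocol 11.4.3 says that cardioversion within 48 hours is not progression.

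**3. The plan's own figure, for scale.** Inputs (Protocol 13.4, SAP 6): 3-year rates of 5% and, after allowance for crossover, 15%; one-sided alpha 0.025; power 85%.
- HR = ln(0.95)/ln(0.85) = 0.3156, so −ln HR = 1.153 (stated 1.154).
- Events (Schoenfeld) = 4 × (1.960 + 1.036)² / 1.153², just over 27, rounded up to 28. This matches the 28 events at the last look in Protocol Table 6.
- Power at D events = Φ(√D/2 × 1.153 − 1.960). At D = 28 this is 86.2%.

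**4. Size under assumed overrule rates.** The documents give no rate, so the following are assumptions: 28 confirmed events; a share q of site calls unconfirmed; 1 to 2 years of follow-up left per affected subject; a later 3-year progression risk r of 5% to 50%; missed events reduce D without changing the HR.
- Unconfirmed subjects m = 28q/(1 − q).
- Expected missed events = m × [1 − (1 − r)^(R/3)], with R years left.

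| q | m | Person-years (1–2 y each) | Expected missed events | Lowest power in range | Power if all m progressed unseen |
|---|---|---|---|---|---|
| 5% | 1.5 | 1.5–2.9 | 0.02–0.55 | 85.6% | 84.4% |
| 10% | 3.1 | 3.1–6.2 | 0.05–1.15 | 84.8% | 82.0% |
| 20% | 7.0 | 7–14 | 0.12–2.59 | 82.8% | 75.3% |

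Example for the last row: 7 × (1 − 0.5^(2/3)) = 7 × 0.370 = 2.59; D = 28 − 2.59 = 25.41; power = Φ(0.947) = 82.8%. The last column is a limit, not an expectation.

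**5. The HRS 2017 analysis.** SAP 8.3 and 10.5 repeat the analysis with persistent AF defined only as AF sustained beyond 7 days. A subject cardioverted between 48 hours and 7 days meets the protocol endpoint and stops monitoring, but has no HRS event. No separate censoring rule is given. If the primary rule is carried over, the same unmonitored time arises here without any disagreement between site and sponsor.

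**The case against.** **The stop rule can be read more narrowly.** Protocol 11.2.1 ties the stop to actually reaching the endpoint, TTM is read by a core lab (11.5), and 11.4.1 and 11.4.2 say that monitoring is not required, not that it must cease. On that reading, an overruled subject has not reached the endpoint and should have stayed on the full schedule. This has some force, but no section describes feedback of the sponsor's decision to the site or a resumption of monitoring.

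**A reader might infer that these subjects are not observed at all.** The documents do not support that. Adverse events are still reported, unscheduled cardiovascular visits need an eCRF (11.2.2), and Table 1 lists TTM and documentation of cardioversion at year 3, with an ECG if done as standard of care. What is lost is the scheduled TTM that looks for asymptomatic episodes. Nor need the interval run to year 3: SAP 5.1 says that the study was terminated early.

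**A reader might infer that a few overruled calls would reverse the primary result.** With Z ≈ (Dc − Dt)/√(Dc + Dt), a 7 v 21 split gives 2.65. Losing four Control events (7 v 17) gives 2.04, and 10 v 21 gives 1.98, both below the 2.0507 at the last look in Table 6. These scenarios need extreme concentration in one arm. Even with 30% of 28 calls overruled, about 8 subjects, a 7:21 split gives 2 Test and 6 Control. Three hidden Test events are then impossible. Four or more missed Control events among 6, each at 1 − 0.5^(1.5/3) = 29% risk, have a probability of about 6.5%, before allowing for any detection. SAP 10.4 also calls that table an example whose bounds are recalculated.

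**Bias is conditional.** Nothing in the documents shows that calls or overrulings differ by arm. That overruled subjects have a raised risk of a later event is plausible but not documented.

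**Censoring at the stop has its own problem.** It removes subjects at the moment of suspected progression, which may be informative. This stands, and it is why that rule belongs in a sensitivity analysis and should not replace the primary rule.

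**Conclusion.** The gap is real. Applied literally, the two documents together count time after the end of required rhythm monitoring as event-free for any subject whose reported progression is not confirmed, and no planned analysis tests the effect. The likely cost in power is modest: at most about 3 to 4 percentage points (86.2% to 82.8%) if 5% to 20% of calls are unconfirmed and later 3-year risk is no more than 50%. The size depends wholly on the overrule rate, which is not given. Bias in the hazard ratio requires a difference between arms in calls or overrulings. That is possible in an open-label trial with sponsor adjudication and about 28 events, but it is not shown. The point justifies added sensitivity analyses and clearer wording. It does not show that the primary analysis is invalid.

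**What to change.** **SAP 8.3 and 10.5.**
- Add a sensitivity log-rank test of the primary endpoint that counts all investigator-determined progressions at the investigator's date.
- Add a second that censors unconfirmed subjects at their last rhythm recording before monitoring stopped.
- Report the number of unconfirmed calls by arm.
- Apply the same last-rhythm-recording censoring check to the HRS 2017 analysis, for subjects cardioverted between 48 hours and 7 days.

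**Protocol 11.2.1, 11.4.1 and 11.4.2.** For any subject still in follow-up, tie the end of scheduled TTM and interim visits to confirmation of the endpoint. Reconcile the TTM stop rule (7 consecutive days) with the endpoint definition (longer than 7 days).

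**Cost.** The SAP changes need some extra analysis on data already planned for listing (adjudication form, ECG, Holter and event recorder). The second test may involve informative censoring and should be read beside the first. The protocol change means that a few subjects transmit for longer while adjudication is pending. The turnaround is not stated, and after early termination the change can help only subjects still being followed.

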9. STUDY SUBJECTS AND DEMOGRAPHICS

9.1 Disposition of Subjects and Withdrawals

All subjects who provide informed consent will be accounted for in this study.

Disposition and study population summaries will be presented for all enrolled subjects by randomized treatment groups. Enrolled subjects are defined according to study protocol section 9.5 as subjects who sign the study informed consent form and are randomized. Thus, the set of enrolled subjects corresponds to the ITT population.

Descriptive summaries of population data will include the following:

- The number of subjects in each study population (ITT, PP, and Safety) will be summarized overall, by treatment group, and by study site.
- A listing sorted by randomized treatment group and subject will be provided that will include the reasons for exclusion from any of the study populations and the treatment assignment for the PP and Safety Population analyses.
- The number of subjects enrolled, excluded, discontinued, prematurely withdrawing from the study, lost to follow-up, died, not completed due to AE,

not completed due to other reasons, completed and the reasons for classification will be summarized.

- A listing of disposition as described above, including further details if available, will be provided for subjects in the ITT population.

A listing of screening failures (which are not randomized) with reason for screening failure will also be added.

9.2 Protocol Violations and Deviations

Protocol deviations are captured in the CRF on a specific protocol deviation CRF page.

Incidences of all protocol deviations reported in the CRF will be summarized by protocol deviation code. A listing of these protocol deviations will also be included.

Each protocol deviation entered to the eCRF will be classified by the sponsor into major and minor from study conduct perspective. The sponsor assessment will be included in the data base extract.

A major deviation will not automatically lead to exclusion of a subject from PP population. Generally, it is planned to exclude a subject only from PP population in case of a major protocol deviation related to inclusion or exclusion criteria. To make a final decision, the sponsor will review all cases with major deviations individually and decide which subjects to exclude from PP population. The sponsor will provide a list of subjects to be excluded from PP population. The sponsor review will be completed before DB lock..

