### 13.6 Analysis Populations

The study contains two treatment arms with subjects receiving either catheter ablation, with or without AAD therapy; or, AAD therapy alone. The following analysis populations will be used to complete the analyses of data:

**Intent to treat subject population (ITT):** The ITT subject population will include all subjects randomized, where subjects will be classified by the group to which they are randomized, regardless of the treatment received. For the ITT population, cross-over subjects will be included in the Control Group per randomization. Lost-to-follow-up and withdrawn / early termination subjects will also be included in the ITT population.

**Per protocol subject population (PP):** The PP subject population will include randomized subjects who satisfy the following criteria, according to the treatment actually received:

- **Test Group:** subjects who
  - have undergone RF ablation,
  - are treated with the study catheter (THERMOCOOL® Catheter Family)
  - are in compliance (no major protocol deviations) with the study protocol, and
  - have been treated for the study-related arrhythmia.
- **Control Group:** subjects who
  - have started an investigator-prescribed AAD and completed the dose-loading period (2 weeks),
  - have not undergone RF ablation,
  - are in compliance (no major protocol deviations) with the study protocol, and
  - have been treated for the study-related arrhythmia.

The analyses conducted in the PP population will be as treated analyses. Subjects who have undergone RF ablation will be included in the Test Group regardless of the original treatment assigned (original randomization). Thus, cross-over subjects will be included in the Test Group for PP analyses.

**Safety Population (SP):** The SP will include all subjects who have undergone insertion of an ablation catheter, either as Test Group or cross-over subjects; and, subjects who started an

investigator-prescribed AAD in the Control Group and did not initiate ablation therapy. Analysis of catheter-related complications will be limited to include only subjects who initiated ablation treatment (catheter insertion) - Test Group and cross-over subjects. Adverse drug reactions will be analysed overall for all the subjects who have taken investigator-prescribed AAD and analyzed separately for cross-over subjects, those in the Test and Control Groups (excluding cross-over patients).

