3.4 Treatment Masking (Blinding)

This is an open-label study.

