7. ANALYSIS POPULATIONS

The following analysis populations will be used to complete the analyses of data.

Cross-over subjects will be handled differently for each type of analysis population, as described subsequently. In general, subjects from the control group who have an ablation procedure after the primary endpoint is met will not be analyzed as cross-over.

Intent to treat (ITT) population: The ITT subject population will include all

subjects randomized, where subjects will be classified by the group to which they are randomized, regardless of the treatment received. For the ITT population, cross-over subjects will be included in the Control Group per randomization. Lost-to-follow-up and withdrawn/early termination subjects will also be included in the ITT population.

Per protocol (PP) population: The PP subject population will include randomized subjects who satisfy the following criteria, according to the treatment actually received:

- **Test Group:** subjects who
 - have undergone RF ablation,
 - are treated with the study catheter (THERMOCOOL[®] Catheter Family),
 - are in compliance (no major protocol deviations that has an impact on scientific value of the study) with the study protocol, and
 - have been treated for the study-related arrhythmia.
- **Control Group:** subjects who
 - have started an investigator-prescribed AAD and completed the dose-loading period (2 weeks),
 - have not undergone RF ablation,
 - are in compliance (no major protocol deviations that have an impact on scientific value of the study) with the study protocol, and
 - have been treated for the study-related arrhythmia.

All analyses conducted in the PP population will be as treated analyses. For descriptive tables and simple inferential models with fixed treatment effects subjects who have undergone RF ablation will be included in the Test Group regardless of the original treatment assigned (original randomization). Thus, cross-over subjects will be included in the Test Group for PP analyses. For more complicated inferential analyses, models will be applied where treatment itself is included as time-dependent covariate (see section 10.2 and 10.6.4). The approach described above applies for all tables which do not summarize data by visit (e.g. for time to event endpoints and other endpoints calculated overall per-patient). For summaries by visit and repeated measurement models, cross-over subjects will be completely excluded.

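### Three different per-protocol exclusion rules, with the last word an unmasked case-by-case sponsor decision in an open-label trial

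*SAP*

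**What the plan says.** The compliance criterion for the PP population is stated three times, differently each time.

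- Protocol 13.6 requires, in both arms, that subjects "are in compliance (no major protocol deviations) with the study protocol".
- SAP 7 adds a qualifier. The Control criterion reads "no major protocol deviations that have an impact on scientific value of the study", and the Test criterion is the same in substance. Neither says how impact is judged.
- SAP 9.2 goes further: "A major deviation will not automatically lead to exclusion of a subject from PP population". Its guide is "Generally, it is planned to exclude a subject only from PP population in case of a major protocol deviation related to inclusion or exclusion criteria". The final step is that "the sponsor will review all cases with major deviations individually and decide which subjects to exclude from PP population".

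The grading on which all three depend is also the sponsor's: "Each protocol deviation entered to the eCRF will be classified by the sponsor into major and minor from study conduct perspective". On timing, "The sponsor review will be completed before DB lock". On masking, SAP 3.4 says "This is an open-label study".

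**The concern.** A per-protocol analysis gives up the protection of randomisation. Its credibility rests on subjects being removed by a rule that does not depend on how they did. Here the rule is not settled, and the final decision is a judgement made in a trial where arm is known and the sponsor has already ruled on who progressed.

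This matters more than usual because Protocol 13.4 and SAP 6 assume that 50% of the drug group will cross over to ablation. Readers will turn to the as-treated PP results to see what ablation does once that dilution is set aside. If PP membership could have been influenced by arm and outcome, a gap between the ITT and PP results cannot be put down to cross-over alone.

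**Working it through.** No calculation settles this point, so the check sets the texts side by side.

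**1. What each rule does with the same subject** (compliance criterion only; the other PP criteria match in Protocol 13.6 and SAP 7)

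| Subject has | Protocol 13.6 | SAP 7 | SAP 9.2 |
|---|---|---|---|
| Major eligibility deviation | Out | Out only if scientific value is affected; no test given | Usually out; sponsor decides |
| Other major deviation | Out | As above | Usually kept; sponsor decides |
| Minor deviation only | Kept | Kept | Kept, on the sponsor's grading |

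The protocol and SAP 9.2 give opposite default answers in the second row. SAP 7 gives no determinate answer in the first two.

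**2. What the sponsor can know when it decides**

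- Arm: the trial is open-label (SAP 3.4).
- Endpoint status: SAP 8.3 has the sponsor adjudicate every progression that investigators report, starting with the interim analyses.
- Interim comparison: Protocol 13.9.2 has the sponsor run the interim analyses and write the report. SAP 4.1 sends the results to the sponsor's own safety monitoring committee.
- Final comparison: not available. SAP 4.2 places final analyses, and release of key results to the sponsor, after database lock.

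Neither document says that those who grade deviations or settle PP exclusions are kept from arm, cross-over or endpoint status. Nor does either say that they are the same people who adjudicate; only the sponsor is named.

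**3. Whether the departure is declared**

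SAP 5.1 lists the treatment of remaining alpha, the new start date for the Test Group, the deleted analyses and the added HRS 2017 sensitivity analysis. The PP rule is not there. SAP 8.1 does flag, where it occurs, a change of population for quality of life. SAP 9.2 carries no such note.

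**4. Which results depend on PP membership**

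- Not exposed: the ITT primary test (Protocol 13.9.1, SAP 10.1), safety (SAP 11) and health care utilisation, which SAP 12.2 puts in ITT.
- Exposed, with an ITT counterpart: the PP Kaplan-Meier analysis, the 1- and 2-year endpoints, repeat ablations and new drugs, rhythm, and the fixed-treatment factor models.
- Exposed, PP only: the Cox model with time-dependent treatment (SAP 10.2), its HRS 2017 repeat (SAP 10.5) and the time-dependent factor models (SAP 10.6.4).
- Quality of life: SAP 8.1 says ITT, but SAP 12.1 and the planned tables (14.2.11.1 to 14.2.12.3) say PP. As listed, there is no ITT table to compare with.

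**5. Why no size is put on it**

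Protocol Table 6 plans 28 events in total and does not split them by as-treated group. At the assumed cross-over, 0.5 × 161 = 80.5 Control subjects would be ablated. Ignoring PP exclusions, the as-treated groups would be 161 + 80.5 = 241.5 and 80.5, a share of 241.5/322 = 0.75 against 0.25 rather than 1:1. An equal-arm calculation on randomised event counts therefore does not describe this population. The Cox models also divide each cross-over subject's time between treatments. The documents do not give the timing of cross-overs or the number of major deviations, and SAP 5.1 says that the study stopped early.

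**The case against.** The case for leaving this alone has real content.

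- **The primary result is safe.** It is ITT, and no alpha is allocated to PP. This stands.
- **The list is closed before lock.** A reader might infer that, in an open-label trial, pre-lock review protects nothing. The documents do not support that: the list is fixed before the final PP comparison is run, so it cannot be tuned to that result. But knowing a subject's arm and whether that subject progressed is enough to influence a judgement, so the protection is partial.
- **The discretion is bounded.** It covers only subjects with a major deviation, and the default concerns eligibility, which is fixed at entry and would be fairly neutral between arms. SAP 9.2 can even be read as giving working content to SAP 7. This would answer much of the concern if the default were binding, but it is worded as a general intention and the sponsor decides each case.
- **Exclusions are visible.** SAP 9.1 lists reasons by randomised arm, and Listings 16.2.4.3 and 16.2.17.1 show major deviations and the endpoint. A protocol-rule PP set could be rebuilt from them. That is disclosure after the event, and it inherits the sponsor's grading.
- **The protocol's rule is not clearly better.** Protocol 13.6 does not define a major deviation. Under Protocol 11.2.1, subjects who progress skip interim visits, so the opportunity for visit deviations itself depends on outcome. This stands, and it is why that rule is proposed below as a check and not as the main rule.

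Two stronger readings are tempting. One is that exclusions were in fact chosen by arm or outcome; the documents show an opening for this, not its use. The other is that removing a few progressors would shift the result by a stated amount; for the reasons in step 5 of the working, they give no basis for such a figure.

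**Conclusion.** The point holds as one of inconsistent definition and absent masking. The compliance rule for PP differs across Protocol 13.6, SAP 7 and SAP 9.2, the change is not recorded in SAP 5, and the operative version leaves the last word to a sponsor that can know arm and outcome. PP membership could therefore be influenced by both.

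The reach is confined to supportive analyses. It is greatest where no ITT counterpart is planned: the time-dependent Cox models, and quality of life if SAP 12.1 and the table list govern. The conclusion assumes that no separate document, outside the protocol and SAP, masks the reviewers or defines the grades.

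**What to change.** 1. State one binding exclusion rule, by protocol deviation code, in identical terms in SAP 7 and SAP 9.2, with no case-by-case override. The existing eligibility guide, made binding, would serve. The other PP criteria in SAP 7 stay as they are.
2. Record the departure from Protocol 13.6, with the reason, in SAP 5.
3. Carry out the major/minor grading, and any judgement the rule still leaves, from a listing without arm, cross-over or endpoint status. If only the final step were masked, the discretion would move back to the grading. Where a deviation's description itself reveals the arm, note that.
4. Repeat the main PP analysis with all major deviations excluded, as the protocol has it, as a sensitivity analysis. This remains possible even if the exclusion list has already been settled.

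Reconciling SAP 8.1 with SAP 12.1 on the quality-of-life population is a linked correction; if ITT is confirmed, those tables leave the exposed set.

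The cost is SAP wording, one masked listing and one extra table. The sponsor gives up its discretion over individual subjects. The primary analysis does not change.
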